The recent Gong work has evaluated the role of lutein / zeaxanthin comparing the data obtained from various studies, including those of Romagnoli, Dani and Manzoni. Furthermore the RCT analysis of Rubin on the subject, it can be concluded that lutein / zeaxanthin are well tolerated and well absorbed from preterm infants also after oral administration.

The extremely interesting result that has emerged although not statistically significant (probably due to the small sample) is that supplementation with lutein / zeaxanthin reduced the incidence and severity of ROP.

Our protocol is born from the idea that given the interesting results of earlier work is considered important to deepen a dosage of at least 1 ml / kg equal to 0,5 mg of lutein and 0.05 mg of zeaxanthin.

It 'important to assess the value of the key markers of oxidative stress biological

antioxidant potential (BPT) and total hydroperoxide (TH) during and after treatment.

Already in a previous work (S. Perrone, M. Longini) has demonstrated a reduction in radicalemia in term infants, during and after administration of lutein / zeaxanthin by determination of the BTP and TH.

Preparation based on lutein ans zeaxanthin have never reveled on humans negative or harmful effects after administration, or to the gastrointestinal or sistemis level. In recent studies there were not reported adverse phenomena after administrating 20 mg/day of lutein or zeaxanthin for a period of 6 months, or interactions with other liposovable nutritive elements.

Justifying the noncommercial character of the study

This study is based on the administration of a dietary supplement of lutein/zeaxanthin. It is included in the category of a spontaneous/non-commercial pilot study, because it is born from the need of private healt care of identifying a natural antioxidant product which may reduce the severeness of the diseases related to the prenatal period, limiting the sufferance of newborns and their families, by reducing simultaneously the charges in SSN pregnancy which arise from the standard treatments and short-term and medium to long-term rehabilitation.

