They contribute and maintain the functionality and integrity of the eye's sensitive structures (retina, iris, lens), preventing or reducing the damages caused by free radicals. In specialized literature is largely described their high antioxidant

	activity and the advantages of a consumption or supplement. Lutein and zeaxanthin pass through the placental barrier, they are also present in the colostrums and breast milk and it is believed that they take part to the embryogenesis of the retina and to the development of visual functions during the first weeks of life. As a result, the lutein and zeaxanthin are essential to the health of the eye, both on adults and children suring their first hours of life. Thus, the absorption of these substances proves to be necessary in situations of necessity growth or in case of deficient intake, both during the aging period of the ocular structures responsible for the visual function (macula), and during their conservation period. The lutein and zeaxanthin do not present contraindications and can be taken at any age. Use: LUTEIN ofta 0,5 gocce is indicated in situations of necessity growth or in case of deficient food intake of its components on different age groups. LUTEIN ofta 0,5 gocce can be useful especially in preventing macular or retina damages.	
Study Objectives	Main objective	
, and a second s	To evaluate if the administration of pharmacology doses of Lutein/Zeaxanthin micronutrients in water (LUTEIN ofta 0,5 gocce – Neoox) is able to reduce the level of radicalemy and at the same time to elevate the antioxidant power of premature newborns (gestational age: \leq of 32 weeks and / or weight at birth: \leq 1500 grams).	
Study scketch	pilot study, non-commercial, with food supplement, treated vs. control with a	
	ratio 1: 1 double-blind. The identical vials, corresponding to placebo and active product, have an alphanumeric code without meaning for the operator, but that identifies the traty from control, in an anonymous document kept by the Statistical. The document will be placed in a sealed and anonymous envelopeand it will be kept open by the statistician at the time of data analysis.	
People	Inclusion criteria	
participating at	• Newborns with a weight ≤ 1.500 grams and/or gestational age ≤ 32 weeks;	
the study and their number	Male and female newborns; Newborns where reports went to sign the information forms informed.	

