number	• Newborns whose parents want to sign the information form – informed consent.	
	Consent	
	Exclusion criteria	
	• Informed consent is not signed	
	 Infants of birth weight ≥ 1.500 gramms and/or gestational age > 32 weeks infants hospitalized after 36 hours of life 	
	Infants with ophthalmologic disease at randomization	
	• infants with severe malformations	
	Number of nationts about to be varietaved	
	Number of patients about to be registered It is expected to register a total number of 50 newborns divided in two groups:	
	• Experimental group A: 25 newborns treated;	
	Control group B: 25 newborns treated.	
Randomization	Subsequently enrollment patients will be randomly divided into Group A and Group B throught a web system that allows the randomization into three different recruitment centers	

	T
Number of centres	Multicenter pilot study. At the study will participate three Italian experimental centres: Naples, Siena and
	Padova.
	The centre from Naples will be the national coordinator and the center from Siena
	will handle in a centralized way the laboratory results. The center from Padova
	will help to recruit an adequate number of cases.
Sample size	BAP and TH are two bio-markers with different hypothetical changes clearly different. For this reason we will use the study method proceeds by the following online site http://clincalc.com/stats/samplesize.aspx (Rosner B. Fundamentals of Biostatistics. 7th ed. Boston, MA: Brooks/Cole; 2011). The inserted reference values are for BAP 2361 (\pm 466) μ mol/L and for TH 156.75 (\pm 64.0) Ucarr (Perrone S., Longini M. et. Al). The difference for BAP that we hypothesize to find is an increase of at least 500 μ mol / L which is approximately 20% of the control data. By setting α = 0.05% and β =0.1% with a power of 90% the number of samples required is 25 + 25 = 50. For the TH assume a decrease of 50 Ucarr which is approximately 30% of the
	data of the control. By setting $\alpha = 0.05\%$ and $\beta = 0.2\%$ with a power of '80% also in this case the required number of samples is $25 + 25 = 50$.
	However $25 + 25$ is the minimum number. Taking into account any ongoing study waivers (parents may request to discontinue treatment at any time) which go beyond statistical calculations. So in case of necessity we will recruit a number of infants to reach the minimum number according to the design of the protocol (25 $+$ 25).
Treatment and	Products administered:

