laboratory investigations foreseen. The second semester will be used to study and analyse the results achieved.

Procedures

Methodology:

When born, premature newborns that are comply with the inclusion parameters will be introduced and separated in two random groups (A and B).

All newborns, during the observation period, will be submitted to the blood collection (1 ml) from the umbilical cord and peripheral (at the same time with the routine collections) on which there will be performed blood gas analysis and oxidative stress markers (TH and BAP). All registered newborns will also be submitted to the verification of their history concerning the examination and collection, in view of evaluation the presence or absence of ROP, NEC, IVH, BPD and infections.

Collection Time

- T0, basic at birth, before begining the treatment: blood collection from the umbilical vein.
- T1, first check, to 15 days after initiation of treatment: peripheral blood collection in view of verifying it before the Lutein/zeaxanthin administration.
- T2, second check, at 30th day since the begining of treatment: peripheral blood collection in view of verifying it before the Lutein/zeaxanthin administration.

The parents will be informed concerning the experimental procedure and the checks schedules.

It will be required the written consent of the parents.

The protocol shall be submitted to approval to the local ethics commission.

Evaluation Parameters:

Efficiency:

a) Evaluation of oxidative stress biomarkers in the peripheral blood of the premature newborn before and after the treatment.

Tolerability:

There will be transcribed on the data sheet possible adverse events which may be observed by the doctor.

Evaluation Scale

- a) Evaluation of the oxidative stress: by deremining the oxidative stress biomarkers and registering them in the data sheet.
- b) They must be indicated:

Demographic Characteristics

- Sex
- Gestational Age
- Weight (with percentile)
- Mode of delivery
- Preeclampsia
- Premature rupture of membranes
- Using steroids before birth
- Using antibiotics before birth
- Use of drugs or harmful substance before birth

Clinical features

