	 Apgar score Use of surfactant Umbilical catheter CVC location and duration Intubation Mechanical ventilation (procedures and time) Supplementation of O2 Incidence of infections Use and type of antibiotics Use and type of antifungal Use and type of post-natal steroids Use and type inotropic Use of NPT Duration of treatment in NICU Nutritional Characteristics: Oral feeding start time Exclusive oral feeding start time Fluid volume Intake calories (protein, carbohydrates and fats) Use of maternal and /or uman milk Other therapies associated and/or permitted During the trial period it is not permitted any product administration or antioxidant activities (anti-radicals) or products which contain even a sole
Basic examination	component having this result, excepting the protocol. At birth, as it is foreseen by newborn protocols, the babies will be submitted to
	several medical examinations.
Control examination	From the Birthing Unit, the newborns will be transered to intensive care rooms where they will be submitted to multiple control examinations.
Follow-up examinations	As it is foreseen in neonatal protocols.
Statistical Analysis	The Student t test for independent data is the type of analysis that will be used to assess statistically significant differences between the parameters recorded in the two groups (treated and control). The Student t test is the method of choice for analysis as it allows to evaluate the values of a continuous random variable measured in not very many samples (25 subjects per group). It will be using the statistical package SPSS system.

REFERENCES

Lutein: description, pharmacokinetics activity and characteristics, mechanism of action, safety and tolerability

- 1. Shao, A. and Hathcock, JN. Risk assessment for the carotenoids lutein and lycopene. Regul Toxicol Pharmacol. 2006 Aug;45(3):289-98.
- 3. Khachik F, de Moura FF, Chew EY, Douglass LW, Ferris FL 3rd, Kim J, Thompson DJ. The effect of lutein and zeaxanthin supplementation on metabolites of these carotenoids in the serum of persons aged 60 or older. Invest Ophthalmol Vis Sci. 2006 Dec;47(12):5234-42.

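### The main objective needs TH down and BAP up together, but the plan names no primary visit and no rule for meeting it, and its printed alpha, beta and TH power do not hold

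*Combined protocol and SAP*

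**What the plan says.** Study Objectives, Main objective, asks whether the supplement "is able to reduce the level of radicalemy and at the same time to elevate the antioxidant power of premature newborns". From the background, TH is the marker for radicalaemia and BAP the marker for antioxidant power, so the aim has two parts and a direction for each.

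Procedures, Collection Time, sets a baseline sample from the umbilical vein (T0) and two peripheral samples later: "T1, first check, to 15 days after initiation of treatment" and "T2, second check, at 30th day since the begining of treatment". The efficacy parameter is "Evaluation of oxidative stress biomarkers in the peripheral blood of the premature newborn before and after the treatment". The background rationale speaks of measuring "antioxidant potential (BPT) and total hydroperoxide (TH) during and after treatment".

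The Sample size section notes that "BAP and TH are two bio-markers with different hypothetical changes clearly different" and does one calculation for each. For BAP it writes "By setting α = 0.05% and β =0.1% with a power of 90" per cent. For TH it gives alpha 0.05%, beta 0.2% and power 80%. Both calculations end at 25 + 25.

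The Statistical Analysis section names one method, the independent-samples t test, which "will be used to assess statistically significant differences between the parameters recorded in the two groups (treated and control"). It gives no primary visit, no order of markers, and no statement on whether one significant marker is enough.

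**The concern.** Two markers at two visits give four comparisons that bear on the main objective. The objective implies that both markers must move, but nothing says so as a rule, and nothing says at which visit. The choice of visit, and even of a single favourable marker, could therefore be made after the results are known. The study sets alpha and power and will read p-values against its objective, so it needs to say beforehand which ones count.

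The figures beside the objective add to the problem. The printed error rates cannot be the ones used, the stated TH power is slightly too high, and no power is given for the objective as it is worded.

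**Working it through.** **Inputs.** From the Sample size section: BAP SD 466 and difference 500 µmol/L; TH SD 64.0 and difference 50 Ucarr; 25 per group. Assumed, because the documents do not say: two-sided tests, and correlations between markers and between visits from 0 to 0.9 in size, with either sign between markers.

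**1. The plan's own sample size.** Normal approximation, n per group = 2(z_alpha/2 + z_beta)²(SD/difference)², with alpha = 0.05.
- TH, 80% power: 2 × (1.960 + 0.842)² × (64/50)² = 25.7, so 26 per group. The plan's 25 is one short of this. With the t distribution it is 27.
- BAP, 90% power: 2 × (1.960 + 1.282)² × (466/500)² = 18.3, so 19 per group (20 with the t distribution). The stated need for 25 does not reproduce, but the error is on the safe side.

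**2. Power at 25 per group.** Noncentral t with 48 degrees of freedom and noncentrality (difference/SD) × √(25/2).
- BAP: 500/466 = 1.073; noncentrality 3.79; power 96.05%.
- TH: 50/64 = 0.781; noncentrality 2.76; power 77.2%.
- At the printed alpha of 0.05% (0.0005): 53.0% for BAP and 18.7% for TH. The stated 90% and 80% are near the 5% results and far from these, so the percent signs on alpha and beta are evidently slips.

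**3. Power for both markers at one named visit.** This lies between 0.9605 + 0.7723 − 1 = 0.733 and the smaller power, 0.772. At independence it is 0.9605 × 0.7723 = 0.742. Taking the plan's stated 90% and 80% instead gives 0.70 to 0.80.

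**4. False success under the joint reading.** Suppose BAP responds as planned at both visits and TH does not respond. The joint objective is then not met. At independence a both-markers rule succeeds by chance in 0.9605 × 0.025 = 2.4% of trials at a named visit, and in 1 − (1 − 0.024)² = 4.7% if either visit may serve. Simulation (100,000 trials per setting):

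| Correlation: markers, visits | Named visit | Visit left open |
|---|---|---|
| 0, 0 | 2.4% | 4.7% |
| −0.3, 0.3 | 2.5% | 4.8% |
| 0.3, 0.3 | 2.2% | 4.2% |
| −0.6, 0.6 | 2.4% | 4.3% |
| 0.6, 0.6 | 1.7% | 3.2% |
| −0.9, 0.9 | 2.5% | 3.6% |
| 0.9, 0.9 | 1.0% | 1.6% |
| −0.9, 0 | 2.5% | 5.0% |
| 0.9, 0 | 1.0% | 1.9% |
| 0, 0.9 | 2.4% | 3.4% |

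In the same scenario BAP alone is significant at a given visit in 96% of trials. The same data therefore count as success or failure depending on the unwritten rule.

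**5. If one favourable marker at either visit were accepted.** With no effect on anything and independence, 1 − 0.975⁴ = 9.6% of trials would show at least one favourable significant result. Over the assumed correlations the simulated range is 5-10%.

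**The case against.** The strongest reply is that the plan nearly answers the question itself. The objective joins the two markers, and sizing each at full alpha suits a rule that both must succeed, which needs no alpha split. No section offers success on one marker. This is also a pilot in 50 infants with biomarker outcomes, where strict family-wise control is less pressing. Much of this stands. It makes both-markers the natural reading and limits the harm, but an aim is not a decision rule, and the visit remains open.

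A reader might infer a family-wise error of up to 1 − 0.95⁴ = 18.5%. The documents do not support that as the size of the problem. It needs one marker to suffice and unfavourable differences to count, both against the stated objective, and it treats repeated samples from the same infants as uncorrelated.

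A reader might also infer that the efficacy wording already fixes T2. It leans that way, but it speaks of peripheral blood before treatment, and the only pre-treatment sample is umbilical. The background wording covers the treatment period as well. T2 is suggested, not named.

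Finally, a reader might blame the joint rule for the whole power shortfall. Joint power is 2.8 to 6.7 points below 80%. TH's own power of 77.2% accounts for 2.8 of these, and requiring both markers adds between 0 and 3.9.

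The observation-period entry is broken in the text available for this review. The objective, sample-size, efficacy and analysis entries, where such a rule would belong, are readable and silent.

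**Conclusion.** The concern holds in a limited form. The plan states a joint, directional objective but gives no primary visit and no written rule for declaring it met. Under the joint reading, the open visit raises false success from about 1-2.5% to about 2-5% when only BAP responds; at worst this doubles the 2.5% directional level. Accepting one marker at either visit, which the objective does not support but the analysis section does not exclude, would give a favourable false positive in about 5-10% of trials with no effect. It would be too strong to say that the plan permits a one-marker success: it merely fails to rule one out.

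Separately, the printed alpha and beta values are wrong as percentages. At two-sided 5%, 25 per group gives 96% power for BAP, 77% for TH rather than the stated 80%, and 73-77% for both. The power figures rest on the plan's own SDs and differences; the error rates also rest on the assumed correlations. The change is worth making, because the plan relies on these figures and the correction is cheap.

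**What to change.** Before the treatment code is opened:

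1. Name one primary visit. The choice is the sponsor's; T2, at the end of treatment, is natural. Declare the main objective met only if TH is lower and BAP is higher in the treated group at that visit, each at two-sided 5%, with no alpha split.
2. Report the other visit and all other parameters as secondary estimates with 95% confidence intervals.
3. Correct the printed alpha to 5% (0.05), and beta to 0.1 for BAP and 0.2 for TH.
4. Restate the power at 25 per group as about 96% (BAP), 77% (TH) and 73-77% (both together).

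The cost is a few sentences, with no more infants, blood samples or measurements. The downside is that the stated power for TH and for the joint objective looks less favourable, and an effect on one marker only, or only at the other visit, will not count as a primary success.
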